 - e. Primary and secondary breast cancer with any hormone status, including ER+, PR+/-, Her2neu-; ER+,PR+/-, Her2neu +; ER-,PR-, Her2neu-; ER-/PR-, Her2neu +

Exclusion criteria

- 1. Previously published research using gene expression data sets for primary breast cancers previously treated with chemotherapy, hormone therapy, or radiation prior to analysis will not be used for the control population
- 2. Previously published research using gene expression data from cell lines and animal studies will not be used for the control population
- 3. Non-epithelial breast malignancies, including lymphoma or sarcoma of the breast and melanoma and non-melanomatous skin cancers
- 4. In situ carcinomas of the breast

Materials/Data needed from the CCSS

- 1. Adequate secondary breast cancer tissue, from the study patients, to yield sufficient, amplifiable mRNA for eventual hybridization with the Affymetrix U133A Gene Chip.
 - a. N=54 (or more if possible)
 - b. At least five 10-micron scrolls (or equivalent quantity) of tumor tissue, verified by corresponding H&E slide, for each sample
- 2. Clinical data on study patients:
 - a. Age at childhood cancer diagnosis
 - b. Childhood primary tumor diagnosis
 - c. Childhood radiotherapy details (including total body irradiation and pelvic radiotherapy)
 - i. Dose and fractionation to irradiated site

- ii. Radiation dose to the chest
- iii. Age at start of radiation
- d. Age at breast cancer diagnosis
- e. Menopausal status at breast cancer diagnosis
- f. Age at death or last follow-up with current vital status for survival calculations
- g. Use of chemotherapy for treatment of the primary cancer

Statistical and Analytic Plans:

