To study our second aim, the molecular subtype status of the study population will be analyzed as a clinicopathologic factor for it's association with survival as well as with other factors such as age at childhood cancer diagnosis, type of childhood primary malignancy, age at time of radiation for childhood malignancy, radiation dose to the chest during childhood, total radiation dose received during childhood, use of chemotherapy for treatment of childhood malignancy, age and menopausal status at breast cancer diagnosis, and stage at breast cancer diagnosis. Correlative analysis (Spearman's rho, t-tests, ect.) will be used to test for univariable associations between the molecular subtype and the cross-sectional demographic variables. For the time-to-event outcomes such as survival and time to onset of breast cancer the log-rank test will be used to determine univariate associations of the molecular subtype (key risk factor of interest) with these outcomes intervals. Additional risk factors such as age at childhood cancer diagnosis, age at time of radiation for childhood malignancy, and radiation dose to the chest during childhood will also be evaluated similarly. Cox proportional hazards models will be used to evaluate multivariable associations between molecular subtype and each of the time-to-event outcomes, adjusting for other factors found to be significant in univariable analyses, or considered *a priori* to be important to include in the model (e.g. age at diagnosis, breast cancer stage, etc.)

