The CCSS database represents the only chance in which the issue of the breast cancer molecular subclass prevalence, in the setting of previous thoracic radiation, could possibly be addressed. If any single institution attempts to do this, there would not be enough cases to draw a statically significant conclusion. Fortunately, there are 54 cases within the CCSS database, and this is sufficient to determine if the 5 molecular subtypes are evenly distributed, or predominately composed of 1 or 2 subtypes. In the most diffuse scenario, if there are at least 10 samples per subtype (5), there will be a >80% power to detect a 2-fold difference between any of the two groups using Chi-squared analysis. A coefficient of variation of 50% and alpha = 0.005 (.05/10, to adjust for 10 comparisons between 5 groups) will be used for the calculations. Since we expect there to be 50% with the Luminal A subtype designation, there will be even greater power to make this conclusion statistically valid. It should be iterated, though, that regardless of statistical power, this is a retrospective study and the large number of subjects from the CCSS provide the only means for attempting to answer this scientific question.

Figures:

Hierarchical clustering of 115 tumour tissues and seven non-malignant tissues using the "intrinsic" gene-set. (A) A scaled-down representation of the entire cluster of 540 genes and 122 tissue samples based on similarities in gene expression. (B) Experimental dendrogram showing the clustering of the tumours into five subgroups. Branches corresponding to tumours with low correlation to any subtype are shown in grey. (C) Gene cluster showing the *ERBB2* oncogene and other co-expressed genes. (D) Gene cluster associated with luminal subtype B. (E) Gene cluster associated with the basal subtype. (F) A gene cluster relevant for the normal breast-like group. (G) Cluster of genes including the oestrogen receptor (*ESRI*) highly expressed in luminal subtype A tumours. Scale bar represents fold-change for any given gene relative to the median level of expression across all samples. PNAS, July 8, 2003, vol. 100, no. 14, 8418–8423. Copyright (2003) National Academy of Sciences, USA.

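### For the second aim, chest radiation dose and two ages are screened against time-to-event outcomes with a log-rank test, which as written means grouping continuous factors and losing power

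*Protocol*

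**What the plan says.** All of this concerns the second aim, in the Statistical and Analytic Plans section of the protocol.

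- **Test for subtype.** For survival and time to breast cancer onset, "the log-rank test will be used to determine univariate associations of the molecular subtype (key risk factor of interest) with these outcomes intervals".
- **Extension to other factors.** The next sentence begins "Additional risk factors such as age at childhood cancer diagnosis" and ends "age at time of radiation for childhood malignancy, and radiation dose to the chest during childhood will also be evaluated similarly". Three factors are therefore to be handled like subtype: two ages and one dose.
- **Use of the result.** Cox regression is named only for the multivariable models, "adjusting for other factors found to be significant in univariable analyses, or considered" important a priori. The examples given for the a priori route are age at diagnosis and breast cancer stage.
- **How the factors are requested.** The list of data needed from the CCSS asks for "Radiation dose to the chest" and "Age at start of radiation", with no categories or cut points. The same list sets the number of cases: "N=54 (or more if possible").

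**The concern.** The log-rank test compares groups. That suits molecular subtype, which is a category. Dose and age are quantities, so applying the same test to them means dividing the women into groups and treating everyone within a group as alike. If risk changes steadily with dose or age, the differences within groups carry information that the test discards.

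With about 54 women and fewer deaths, there is little information to spare. A real gradient could fail the univariable screen and then be left out of the multivariable model unless someone had chosen that factor a priori.

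The point concerns the choice of test, not the absence of cut points. Cut points could properly be left to a statistical analysis plan, but supplying them would keep the loss.

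**Working it through.** **The plan's own figure.** There is none for these tests: no number of deaths, hazard ratio, power, cut point or significance level. The only adjusted level in the protocol, "alpha = 0.005 (.05/10, to adjust for 10 comparisons between 5 groups"), belongs to the subtype comparison.

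**Inputs.** From the protocol: 54 cases. Assumed: two-sided 0.05; deaths in 30% (54 × 0.30 ≈ 16) or 50% (54 × 0.50 = 27); a normal or uniform covariate; a log-linear effect.

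**Step 1: information kept by grouping.** With k equal groups, the share kept is the between-group part of the covariate's variance. For more than two groups, an unordered log-rank test also pays for its extra degrees of freedom. The share is therefore scaled by the ratio of noncentralities needed for 80% power on 1 versus k − 1 degrees of freedom (0.815 for three groups, 0.720 for four).

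| Grouping | Normal covariate | Uniform covariate (1 − 1/k²) |
|---|---|---|
| Median split | 2/π = 0.637, loss 36% | 0.750, loss 25% |
| Tertiles | 0.793 × 0.815 = 0.646, loss 35% | 0.889 × 0.815 = 0.724, loss 28% |
| Quartiles | 0.861 × 0.720 = 0.620, loss 38% | 0.9375 × 0.720 = 0.675, loss 33% |

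For an off-centre split of a normal covariate at proportion p, the share is φ(z_p)² / [p(1 − p)]. This gives 0.576 at p = 0.30 (loss 42%) and 0.490 at p = 0.20 (loss 51%). The range is therefore 25% to about 50%.

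**Step 2: power for survival, large-sample formula.** Power ≈ Φ(√D × ln HR − 1.96), with D deaths and HR per SD. For a median split, D becomes D × 2/π. At HR 2.0 (ln HR = 0.693):

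- Continuous, D = 16: 4.00 × 0.693 − 1.96 = 0.81, power 79%.
- Continuous, D = 27: 5.20 × 0.693 − 1.96 = 1.64, power 95%.
- Median split, D = 16: √10.19 × 0.693 − 1.96 = 0.25, power 60%.
- Median split, D = 27: √17.19 × 0.693 − 1.96 = 0.91, power 82%.

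**Step 3: simulation.** The formula is somewhat optimistic at this size, so the comparison was simulated with n = 54, a normal covariate, exponential survival and administrative censoring. The Cox score test on the continuous value was set against the median-split log-rank test.

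| HR per SD | Deaths | Continuous | Median split |
|---|---|---|---|
| 1.65 | 30% | 50% | 32–34% |
| 1.65 | 50% | 70–72% | 50% |
| 2.0 | 30% | 76% | 53% |
| 2.0 | 50% | 93% | 75% |

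The 53% falls to about 50% if follow-up is cut at exactly 16 deaths instead of at a common time. With no effect, both tests reject in about 5% of studies.

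**Step 4: time to breast cancer onset.** Every case has this event, so D = 54. At HR 2.0 per SD the simulated power is 99% against 93%. The gap is smaller because both tests are near their ceiling.

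**Step 5: when the effect is not log-linear.** If risk steps up at the median with a hazard ratio of 3, the order reverses: 38% continuous against 42% median split with 30% deaths, and 59% against 69% with 50% deaths.

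**The case against.** **The wording is loose.** The protocol mentions no cut or grouping, and the extension could mean only that some univariable time-to-event test will be used. The log-rank test is itself the Cox score test for a group indicator, so a sympathetic analyst might fit a univariable Cox model. That reading is possible. Still, the log-rank test is the only univariable test named, and Cox regression appears only for the multivariable models.

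**The role is secondary.** Subtype is the plan's key risk factor, and dose and the ages are additional ones. Factors may also enter the Cox model by a priori choice, and nothing stops them entering as continuous terms. This stands, and it limits the importance of the point.

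**The size is assumed.** The dose distribution, number of deaths and effect size are not in the protocol, and a threshold effect would favour the median split. This also stands.

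**Stronger readings that the protocol does not support.** A reader might infer that the screen inflates false positives. Searching the middle 60% of cuts for the best-looking one would do so, at about 29% to 32% instead of 5%. However, the plan describes no such search, and a fixed median cut stays near 5%. A reader might also infer that dose is the exposure the study is about. Yet thoracic radiation is an inclusion criterion for every case, the primary endpoint is expression pattern and subtype distribution, and neither specific aim poses a dose-response question.

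**Conclusion.** The point holds as a modest one. Taken as written, the plan applies a grouped test to three naturally continuous factors when a better test is available at almost no cost. If the effect is log-linear, the loss is roughly a quarter to a half of the information. At a hazard ratio of 2.0 per SD, that is about 18 to 23 percentage points of power for survival (93 − 75 and 76 − 53) and about 6 for time to onset (99 − 93).

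These sizes rest on the assumed event fractions, covariate distribution, significance level and log-linear shape. The consequence is confined to the univariable screen and to any covariate it wrongly leaves out of the second-aim Cox model.

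**What to change.** Keep the log-rank test for molecular subtype and other categorical factors. For chest dose, age at radiation and age at the childhood cancer diagnosis, state that the univariable analysis is a Cox model with the factor as a continuous term, plus a check for non-linearity. Use groups for display only, with cuts fixed before survival data are seen.

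The cost is a sentence or two in the analysis section and no new data. The trade-off is that the continuous test assumes a log-linear effect and has less power than a median split if the truth is a threshold near the median. With about 16 to 27 deaths, the non-linearity check will itself have limited power, so it reduces this risk without removing it.

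### One covariate rule serves both survival and time to onset, so the adjusted onset model can condition on age at breast cancer diagnosis, the end point of the onset interval

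*Protocol*

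**What the plan says.** The text is the paragraph on the second aim under Statistical and Analytic Plans in the protocol.

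- **Outcomes.** It speaks of "time-to-event outcomes such as survival and time to onset of breast cancer". Each is first tested against molecular subtype by log-rank.
- **Cox models.** "Cox proportional hazards models will be used to evaluate multivariable associations between molecular subtype and each of the time-to-event outcomes". The onset model is not excepted.
- **Covariates.** There are two routes into the model. One is "adjusting for other factors found to be significant in univariable analyses". The other is a judgement made in advance that a factor is "to be important to include in the model (e.g. age at diagnosis, breast cancer stage, etc".
- **Factors mentioned.** The opening sentence of the paragraph lists, among others, "age and menopausal status at breast cancer diagnosis, and stage at breast cancer diagnosis". The time-to-event screen names three childhood factors. The first is the woman's age when her childhood cancer was diagnosed; the other two stand in the words "age at time of radiation for childhood malignancy, and radiation dose to the chest during childhood will also be evaluated similarly".

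Under Analysis framework, overall survival is defined as starting at breast cancer diagnosis. No time origin is given for onset. Age at start of radiation, age at childhood cancer diagnosis and age at breast cancer diagnosis are all on the list of data requested.

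**The concern.** A covariate in a time-to-event model should be known when the clock starts. For survival after breast cancer, age and stage at that cancer's diagnosis meet this condition. For time to onset they do not, because they become known only when the event happens. Age at breast cancer diagnosis goes further: it is the end of the interval being modelled. A model that holds it fixed asks whether subtypes differ in latency among women diagnosed at the same age, which removes most of the latency difference it is meant to detect.

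At stake is the adjusted association between subtype and onset. Subtype is the plan's key risk factor, and the second aim asks whether radiation speeds the development of breast cancers. Onset is the outcome that bears on that question.

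**Working it through.** The protocol gives no figure for the Cox models, so there is none to reproduce. The check uses an identity and simulation.

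**Inputs from the protocol.** There are 54 cases. All have had breast cancer, so every woman has the onset event and none is censored. About 20% are expected to be Basal under Specific Aim 1: 0.20 × 54 = 10.8, or about 11.

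**Assumed inputs, not in the protocol.** Onset is counted from radiation. Age at radiation is uniform on 5-18 years and unrelated to latency. Latency has mean 20 and SD 6 years. Tests are two-sided at 5%.

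**Step 1: identity.** Let T be time to onset, A0 age at the time origin and A1 age at breast cancer diagnosis. Then T = A1 − A0. The same form holds whether the origin is radiation or childhood diagnosis.

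**Step 2: how much of T is in A1.** If A0 and T are unrelated, corr(A1, T) = √[Var(T) / (Var(T) + Var(A0))]. Here Var(A0) = 13²/12 = 14.1 and Var(T) = 36, so the correlation is √(36/50.1) = 0.85. A1 is largely the outcome itself.

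**Step 3: effect on the subtype test when A1 is added.**

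| True Basal latency | Power, subtype alone | Power, subtype + A1 | Median hazard ratio |
|---|---|---|---|
| 4 years shorter | about 45% (43-46% across runs) | about 21% (20-22%) | 2.0 to 1.5 |
| 6 years shorter | about 78% | 30-33% | 2.9 to 1.8 |

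**Step 4: other assumptions.** Weibull onset (shape 3, mean 20), two equal subtype groups, age at radiation with mean 14 and SD 2 or 4:

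- At a subtype hazard ratio of 2, power falls from about 64-67% to 12-24%.
- At a hazard ratio of 3, it falls from about 96% to 17-40%.
- With no subtype effect, false positives rise to 8-13%.
- The loss is greater at SD 2 than at SD 4 (12% against 24% at hazard ratio 2). The narrower the spread of age at radiation, the closer A1 is to T.

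**Step 5: both ages in the model.** With coefficients −β on A1 and +β on A0, the linear predictor is −β(A1 − A0) = −βT. At each event the woman who fails has the shortest T in her risk set. With untied times, every term of the partial likelihood therefore tends to 1 as β grows, and there is no finite maximum. With exact ages, standard software returned no finite fit, and the likelihood-ratio test for age at radiation was significant in 100% of runs although its true effect was zero. With ages in whole years it was significant in 97-99% of runs, and subtype power was 5-8%.

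**Step 6: stage.** Simulated as unrelated to onset time, stage did no harm. Subtype power with and without it was 65% and 64% at hazard ratio 2, and 96% and 96% at hazard ratio 3.

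**Step 7: A1 left out** (subtype + age at radiation, Weibull setting). Age at radiation is significant in 5-7% of runs and subtype false positives are 5-7%. Power is about 61-66% at hazard ratio 2 and 95-96% at hazard ratio 3.

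**The case against.** Much can be said for the plan, and it limits the point.

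- **The a priori covariates are only examples, and the diagnosis is not named.** True. If childhood cancer diagnosis were meant, that phrase would create no circularity. But the paragraph spells out childhood cancer diagnosis when it means it, and here the phrase stands next to breast cancer stage. Breast cancer diagnosis is the natural reading.
- **The choice of covariates belongs in an analysis plan.** Often so. But the protocol states a rule here and extends it to every time-to-event outcome.
- **Age at radiation.** A reader might infer that it will come out significant every time. The protocol does not support this. It needs that age and age at breast cancer diagnosis in the same model, with onset counted from radiation. No origin is stated and age at radiation is not forced in. With no true effect it passes a univariable screen in only about 5% of runs. With exact ages the sign may be a failed fit, which an analyst would notice.
- **Stage.** A reader might call this self-adjustment too. It is not: stage is no component of onset time. The objection is only that stage is unknown at the time origin.
- **The screening route.** Tested alone against onset, age at breast cancer diagnosis is significant in practically all simulated datasets (99.75-100% across the latency spreads and age ranges tried), so it might seem bound to enter. But the factors named for that screen are all fixed in childhood. Age at breast cancer diagnosis appears in the list of factors to be related to subtype. The wording leaves the screen open but does not put that age in it.
- **Subtype effects on onset are not lost altogether.** The log-rank test of subtype uses no covariates and is untouched.
- **Onset is not a listed endpoint.** The primary endpoint concerns gene expression and subtype distribution; the secondary ones are overall survival and demographics. This stands, and it lowers the severity.

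**Conclusion.** The rule is wrong as written for one of its two outcomes. Read naturally, it offers age at breast cancer diagnosis as a covariate for an interval that ends at that diagnosis, and this weakens the adjusted subtype effect even if no other age is in the model. Under the assumed inputs, roughly half or more of the power is lost: 45% to 21% for a 4-year difference and 78% to 30-33% for a 6-year difference. The direction follows from the identity. The size depends on the latency, its spread, the ages at radiation and the effect, none of which the protocol gives. Breakdown of the fit, or a spurious effect of age at the origin, arises only if both ages are in the model. The severity is low: the damage is confined to the adjusted onset analysis, while the survival model is properly adjusted for the same factors.

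**What to change.** Replace the single rule with one adjustment set for each outcome.

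- **Onset.** State the time origin (start of radiation or childhood cancer diagnosis). Restrict the Cox model to factors known by the end of childhood treatment: age at radiation, chest dose, childhood diagnosis and chemotherapy. Say that age, menopausal status and stage at breast cancer diagnosis are not covariates in it by either route.
- **Survival.** Keep age, menopausal status and stage at breast cancer diagnosis as candidate covariates for this model only, and write age at breast cancer diagnosis in full.

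The cost is a sentence or two in the analysis plan. The onset covariates are already among the data requested, so no further data are needed.

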Our overriding hypothesis is that radiation interacts, enhances, and potentially accelerates the individual patient's genetic predisposition to develop breast cancer, but does not fundamentally alter the molecular phenotype. To test this hypothesis, we plan to obtain the 54 (or more if available) formalin-fixed, paraffin-embedded tissue samples of the secondary breast cancer cases from the CCSS bio-repository from women who received thoracic radiation. We plan to subject these samples to RNA extraction, using established protocols that yield expression profiles that are highly concordant with frozen tissue.¹²⁻¹³ This mRNA will then be assayed for quality and quantity and amplified accordingly.¹⁴ The resultant cDNA will then be hybridized, at our core facility, using the Affymetrix U133A gene chip. Using the GeneSpring software platform, gene expression data will then be analyzed using supervised methods (which will query the expression levels of specific, hallmark genes that define the molecular subtypes of breast cancer) as well as unsupervised methods (within the set of 54 cases as well as in conjunction with 1,619 general population cases) to determine the prevalence of known, and potentially novel, molecular subclasses of these secondary tumors. Once the subclass designation is established for the 54 secondary breast cancers, the patient demographics and overall survival time after diagnoses will be compared to their spontaneous/general population

counterparts. Generating this working data will enable us to answer the following clinically important questions, which represent our specific aims:

- Specific Aim 1: What is the prevalence/distribution of Luminal A, Luminal B, Basal, Her2-enriched and breast-like breast cancer subtypes among those women who received thoracic radiation during childhood for their pediatric malignancy versus that observed in the general population of spontaneous breast cancers? Consistent with our overriding hypothesis is that the prevalence of these molecular subtypes will approximate that observed in the general, spontaneous breast cancer population. Therefore, assuming radiation induced breast cancers are representative of the general population, approximately 50% will be Luminal A, 20% will be Luminal B, 20% will be Basal, and 10% will be Her 2+.

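### The overall-survival Cox model puts about 6 to 7 parameters on an unstated, probably small, number of deaths; subtype hazard ratios may have no finite estimate and a likelihood-ratio test would be too liberal

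*Protocol*

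**What the plan says.** The second-aim paragraph of Statistical and Analytic Plans (Protocol) states that "the molecular subtype status of the study population will be analyzed as a clinicopathologic factor" for association with survival and other characteristics. The number of cases, under Materials/Data needed from the CCSS, is "N=54 (or more if possible").

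Subtype is first tested by log-rank. Multivariable Cox models follow for each time-to-event outcome, "adjusting for other factors found to be significant in univariable analyses", or thought beforehand to be "important to include in the model (e.g. age at diagnosis, breast cancer stage, etc".) The candidate factors include "age at childhood cancer diagnosis, type of childhood primary malignancy, age at time of radiation for childhood malignancy, radiation dose to the chest during childhood", followed by total dose, chemotherapy, menopausal status, and age and stage at breast cancer diagnosis. Three of them are named as examples of factors that "will also be evaluated similarly" against the time-to-event outcomes.

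Specific Aim 1 expects that "approximately 50% will be Luminal A, 20% will be Luminal B, 20% will be Basal, and 10% will be Her 2"+. The power paragraph works with five subtypes: it calls the 54 cases "sufficient to determine if the 5 molecular subtypes are evenly distributed". It gives no expected deaths, follow-up or power for survival.

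**The concern.** The model has many terms for the information that 54 women can supply on overall survival. Subtype alone takes 3 or 4 degrees of freedom, age and stage take 2 to 4 more, and the screening rule can add further terms. The smallest expected subtype has about 5 women. If none of them dies, ordinary partial likelihood has no finite hazard ratio for that group, and large-sample tests on such a model need not hold their nominal level.

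The within-case half of Specific Aim 2, whether survival differs between subtypes among irradiated survivors, leans on this model. A hazard ratio that is extreme because of sparse data could be read as a biological difference, in a population that the protocol says cannot readily be studied elsewhere.

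**Working it through.** **The plan's own figure.** The only power statement (above 80%, 10 per subtype, 2-fold difference, coefficient of variation 50%, alpha 0.05/10 = 0.005) concerns subtype groups and does not bear on the Cox model. There is no survival figure to reproduce.

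**Inputs from the protocol.** 54 cases; four or five subtypes; expected shares 50/20/20/10%, so 27, 10.8, 10.8 and 5.4 women (27/11/11/5 used); age and stage always in the model; about seven other candidates.

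**Assumptions.** 10 to 27 deaths; 5% level for screening and for the subtype test; 50/18/18/9/5% when five subtypes are used; stage mix and covariate correlations.

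**Parameters before screening.**
- Four subtypes, three stage terms: 3 + 1 + 3 = 7
- Five subtypes, one stage term: 4 + 1 + 1 = 6
- Extremes: 3 + 1 + 1 = 5 and 4 + 1 + 3 = 8

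Screening adds about 0.4 on average.

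**Deaths per parameter (deaths/7 to deaths/6), and precision.** For basal v Luminal A, about 70% of deaths fall in the pair, split 2/7 and 5/7. Before adjustment, the 95% interval factor is exp(1.96/√(0.7 × deaths × 2/7 × 5/7)).

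| Deaths | Per parameter | Interval: HR × or ÷ |
|---|---|---|
| 10 | 1.4–1.7 | 5.2 |
| 15 | 2.1–2.5 | 3.8 |
| 20 | 2.9–3.3 | 3.2 |
| 27 | 3.9–4.5 | 2.7 |

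The Schoenfeld formula gives 13 to 28% power for a hazard ratio of 2 in this contrast.

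**No finite estimate.** If each woman dies with probability p whatever her subtype, the chance that at least one of the groups of 5, 11 and 11 has no deaths is 1 − [1 − (1−p)^5] × [1 − (1−p)^11]². The group of 27 is negligible.
- p = 0.2: 1 − 0.672 × 0.914² = 44%
- p = 0.3: 1 − 0.832 × 0.980² = 20%
- p = 0.4: 1 − 0.922 × 0.996² = 8%

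Simulation of the full rule (1,500 runs per level, about 11/16/21 deaths) gave an effectively infinite subtype hazard ratio in 44/21/10% of runs. Over a wider grid (10/15/20/27 deaths) the figures were 53/28/14/5% with four subtypes and 84/63/45/28% with five.

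**False-positive rate for subtype when it has no effect (nominal 5%).**

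| Analysis | About 11 deaths | About 16 | About 21 |
|---|---|---|---|
| Rule as written, likelihood-ratio | 9.7% | 8.1% | 8.2% |
| Screening removed, age and stage fixed, likelihood-ratio | 8.7% | 7.5% | 7.3% |
| Rule as written, global Wald | 1.7% | 3.3% | 4.4% |
| Age and stage fixed, Firth | 3.7% | 4.9% | 5.8% |

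The Monte Carlo standard error at 1,500 runs is about √(0.09 × 0.91/1500) = 0.7 points. No Firth estimate was infinite. Across the wider grid the likelihood-ratio rate was 7 to 12% with screening and 6 to 11% without; the global Wald rate was 1.5 to 8%, mostly below 5%.

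**Time to onset.** All 54 cases have the event, so there are 54/7 to 54/6, or 7.7 to 9.0, events per parameter.

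**Stage.** The second-aim paragraph uses it as an adjustment factor, but the clinical data list (items a to g) under Materials/Data needed from the CCSS does not request it.

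**The case against.** The strongest reply is that the screening clause does little harm. That stands: removing it lowers the likelihood-ratio rate by 1 point or less, close to simulation error. A reader might infer that data-driven selection produces the false positives; the calculations do not support this. Few deaths and small groups do, and the unadjusted log-rank test shows the same pattern (5–7% with four groups, 9–11% with five).

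A reader might also infer that the plan's p-values are too small in general. The protocol names no test for the Cox model, and the global Wald test is mostly below 5%. Single subtype contrasts read at 5% without adjustment give 9–23%, but no such reading is planned. Nor are the hazard ratios arbitrary: they are imprecise and sometimes not estimable, as 54 women with a group of 5 would largely imply under any model.

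Third, the number of deaths, the screening level and a limit on model size can be left to a statistical analysis plan, and so can penalised fitting, which the protocol does not exclude. This also stands, and their absence is not the point. The point is the model that the protocol does commit to, which on its plain reading is an ordinary Cox fit.

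Finally, overall survival is a secondary endpoint, more than 54 cases may be found, and the power paragraph concedes the limits of a retrospective study. These limit the weight of the point without removing it.

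**Conclusion.** The concern holds for overall survival in the cases, and only there. With 6 to 7 parameters and an assumed 10 to 27 deaths, the model has roughly 1.5 to 4.5 deaths per parameter. Under ordinary partial likelihood a subtype hazard ratio is then often not finite (44/21/10% of datasets at about 11/16/21 deaths with four subtypes, more with five), and a likelihood-ratio test of subtype runs at about 7 to 12%.

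These figures rest on assumed deaths, the expected subtype shares, a 5% level and the choice of test. None is a property that the protocol states. With many more deaths the problem would shrink. It does not extend to time to onset.

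**What to change.** For overall survival:

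1. Replace univariable selection with a fixed adjustment set: age at breast cancer diagnosis and stage.
2. Add stage at breast cancer diagnosis to the clinical data list under Materials/Data needed from the CCSS.
3. Fit by Firth-penalised partial likelihood, with penalised likelihood-ratio tests for subtype.
4. Report the remaining factors one at a time, as descriptive results.

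Step 1 alone is not enough, since the false-positive rate barely moves; step 3 does the work. Merging subtypes when deaths are few is not recommended here, because it would give up the comparison between subclasses that Specific Aim 2 asks for.

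The cost is a change of wording, one more data item and a standard software option. The downside is that confounders outside the fixed set are not adjusted for. Penalisation gives finite estimates, but it cannot supply missing information: hazard ratios will stay imprecise and should be reported with their intervals.
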